Atrial fibrillation (AF) is a major cause of cardiovascular morbidity and mortality, affecting more than 46 million people worldwide.¹ Direct current cardioversion (DCCV) is used to terminate an episode of symptomatic or hemodynamically unstable AF. The success rate for DCCV is 90-95% and is dependent on patient and procedural characteristics including obesity, use of antiarrhythmic drugs, pad placement, type of shock waveform and shock energy. Biphasic defibrillation waveform shocks improve DCCV success rates for AF to normal sinus rhythm (NSR) compared to monophasic shocks. Various biphasic shock waveforms are available: The Rectilinear Biphasic Waveform (RBW) is used by the Zoll series R defibrillator while the Biphasic Truncated Waveform (BTW) is used in the FDA approved Lifepak model 15 and 20 defibrillators. Despite their routine use in clinical practice, no adequately powered prospective head-to-head randomized controlled trials (RCT) have compared the safety or efficacy of the two biphasic waveforms for DCCV of AF to NSR.

The primary objectives for this pragmatic prospective randomized controlled trial are to 1) compare the efficacy of first shock DCCV from AF to NSR using anterolateral pad placement and a full-output 200J RBW synchronized shock from a Zoll series R defibrillator or a full output 360J BTW synchronized shock from a Lifepak 15 or 20 defibrillator; 2) compare the DCCV efficacy of first or second full output shock 3) compare the DCCV efficacy of third or fourth full output shock after treatment group cross over after first failing 2 consecutive full output shocks from the originally assigned treatment group. The secondary objective is to compare the frequency of skin irritation or damage after first or second shock cardioversion from either defibrillator.

Data will be derived from approximately 560 patients arriving to Inova sites of care in AF scheduled to undergo either AF ablation with expected DCCV or elective stand-alone AF DCCV. Patients will be included if they are in AF prior to their procedure and are willing to sign the consent form and comply with the research procedures. Participants will be excluded if they are in a rhythm other than AF on arrival to IHVI, have not been appropriately anticoagulated with warfarin or direct oral anticoagulant, or have known left atrial appendage thrombus prior to their procedure.

ABBREVIATIONS AND DEFINITIONS

Abbreviation	Definition of Terms
DCCV	Direct Current Cardioversion

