Efficacy Evaluations:	
 1. Proportion of patients in NSR by ECG or monitor 1 minute after the first DCCV shock. 2. Proportion of patients in NSR by ECG or monitor 1 minute after the first or second DCCV shock. 3. Proportion of patients in NSR by ECG or monitor 1 minute after a third or fourth crossover treatment assignment shock after failing first and second shock on original treatment assignment.
Safety Evaluations:	
 1. Number of patients with skin redness, pain or discomfort under the shock electrodes (excluding those with cross-over) 2. Number of patients with arrhythmic events (asystole, atrioventricular block, transient bradycardia or ventricular arrhythmia) within 10 minutes of the last DCCV shock 3. Frequency of pacemaker or ICD dysfunction after shock among patients with prior pacemaker or defibrillator implant
Statistical and Analytical Plan:	
Based on the best available literature we expect the first shock DCCV success rate to be 93% in our population. A total sample size of 538 subjects (269 in each group) will be needed to provide 80% power to reject the null hypothesis (a difference of efficacy < 5%). The analysis will be performed on the intention-to-treat population. The proportions will be compared using both risk difference and risk ratio with corresponding 95% CI. Effects of treatment will be estimated by modified

A Pragmatic Randomized Clinical Trial Comparing Rectilinear Biphasic Waveform and Biphasic Truncated Exponential Waveform Shocks for Cardioversion of Atrial Fibrillation (Zoll vs Lifepak-RCT) |

PI: [name]

	Poisson regression using generalized estimating equations. Outcomes will be compared across pre-specified subgroups and testing will be performed for interactions (sex, body mass index, first or > 1 AF episode, AF type, DCCV location).
Data and Safety Monitoring Plan:	The study PI will be responsible for study safety. One interval analysis will be performed after 50% trial enrollment. No DSMB will be assembled.

TABLE OF CONTENTS

STUDY TITLE.....	Error! Bookmark not defined.
SUMMARY OF CHANGES	i
ABSTRACT	ii
ABBREVIATIONS AND DEFINITIONS.....	iii
PROTOCOL SYNOPSIS	iv
TABLE OF CONTENTS	viii
SCHEMA EXAMPLES.....	Error! Bookmark not defined.
1. BACKGROUND.....	2
1.1 Study Disease(s) or Condition(s)	2
1.2 Product(s) / Agent(s)	2
1.3 Rationale	3
1.4 Relevant Literature and Data	3
1.5 Correlative Studies Background	5
1.6 Compliance Statement.....	5

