17.2	Participant Discontinuation/Withdrawal from the Study	17
17.3	Early Termination Study Visit	Error! Bookmark not defined.
18.	RECORDINGS.....	18
19.	IRB REVIEW HISTORY	18
20.	COORDINATING CENTER for MULTI-Site Studies	18
20.1	Participating Sites	18
20.2	Description of Collecting Sites.....	18
20.3	Study-Wide Number of Participants.....	18
20.4	Communication to Participating Sites	18
21.	REFERENCES / BIBLIOGRAPHY	18

A Pragmatic Randomized Clinical Trial Comparing Rectilinear Biphasic Waveform and Biphasic Truncated Exponential Waveform Shocks for Cardioversion of Atrial Fibrillation (Zoll vs Lifepak-RCT) |

PI: [name]

A Pragmatic Randomized Clinical Trial Comparing Rectilinear Biphasic Waveform and Biphasic Truncated Exponential Waveform Shocks for Cardioversion of Atrial Fibrillation (Zoll vs Lifepak-RCT) |

PI: [name]

Study Phase	Screening (Pre-Op)	Treatment/Intervention (EP Lab or CDU Procedure Suite)
Informed Consent/Assent	X	
Review Inclusion/Exclusion Criteria	X	
Duration of AF Assessment (< 7 days, 7 days-365 days, > 365 days)	X	
Months since AF diagnosis	X	
Prior DCCV?	X	
CHA2DS2VASC score	X	
Moderate or Severe Valvular Disease?	X	
Heart Failure with Reduced Ejection Fraction?	X	
Body Mass Index	X	
Date of Birth	X	
Sex	X	
Pregnancy Test	X	
Amiodarone (yes/no)	X	
Flecainide (yes/no)	X	
Beta blockers (yes/no)	X	
ACE Inhibitor or ARB (yes/no)	X	
Randomization	X	
DCCV		X
ECG or Monitor 1 minute after 1 st shock		X
Adverse Event Assessment 10 minutes after shock or at conclusion of procedure		X

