5. INVESTIGATIONAL PLAN

5.1 General Schema of Study Design

5.1.1 Hypothesis

We hypothesize that the maximal output first shock efficacy of RBW and BTE shocks differs by more than 5%.

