5.1.3 Study Treatment

Patients with AF will be randomized to receive either a full output synchronized 200J shock using a RBW waveform from a Zoll R series defibrillator or a full output synchronized 360J shock using a BTE waveform from a Lifepak Series 15/20 defibrillator.

A Pragmatic Randomized Clinical Trial Comparing Rectilinear Biphasic Waveform and Biphasic Truncated Exponential Waveform Shocks for Cardioversion of Atrial Fibrillation (Zoll vs Lifepak-RCT) |

PI: [name]

Success will be defined as NSR 1 minute after the shock. Patients who do not have first shock success will have a second full output shock ≥ 1 minute after the first shock.

Patients who do not have success after a second full output shock will be crossed over to the other defibrillator waveform and receive up to 2 full output shocks with a minimum of 1 minute between each shock to ascertain the outcome of the immediately prior shock.

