12. DATA ANALYTICS

12.1 Study Endpoints

Efficacy assessments for the primary endpoints will occur using data obtained at screening and the DCCV study visit. Specifically, the endpoint of NSR will be acquired by monitoring strip or 12 lead ECG 1 minute after each DCCV shock is delivered.

Primary Endpoints

- 12.1.1 The frequency of NSR one minute after a single full output DCCV shock is delivered by a Zoll Series R RBW waveform defibrillator and a Lifepak Series 15/20 BTE waveform defibrillator.
- 12.1.2 The frequency of NSR one minute after the first or second full output DCCV shock is delivered by a Zoll Series R RBW waveform defibrillator and a Lifepak Series 15/20 BTE waveform defibrillator.
- 12.1.3 The frequency of NSR one minute after the first or second full output DCCV shock is delivered by a Zoll Series R RBW waveform defibrillator and a Lifepak Series 15/20 BTE waveform defibrillator after crossing over from the alternative defibrillator after failing 2 consecutive full output shocks at maximum output.

Secondary Endpoints

- 12.1.4 The frequency of adverse events including skin irritation, pain, or burning; arrhythmic events including asystole, atrioventricular block, transient bradycardia or ventricular arrhythmia within 10 minutes of the last DCCV shock; and the frequency of pacemaker or ICD dysfunction after shock among patients with prior pacemaker or defibrillator implant. Transient bradycardia will be defined as symptomatic bradycardia requiring the use of temporary pacing, atropine, isuprel, or epinephrine for rate support. The secondary safety endpoint will be assessed only among patients who do not cross-over from one defibrillator to the other.

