12.2 Analytics

All analyses will be performed on an intention to treat basis. We calculated the sample size on the basis of the 3 prior randomized studies that compared RBW and BTE shocks for DCCV of AF. In these studies, the mean overall shock success was 90-97% and the first shock success varied from 54%-90% albeit the first shock was delivered at a lower energy than maximum output. We therefore estimate that the mean first shock success rate will be 93%. A clinically meaningful difference in first full output shock efficacy is 5%. A total study sample size of 544 patients (272 in each group) is needed to provide a power of 80% to reject the null hypothesis (a difference in efficacy of < 5%).

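### Three endpoints are labelled primary with no testing order, although the hypothesis and sample size cover only the first shock, and the third endpoint compares groups selected by outcome after randomisation.

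*Combined protocol and SAP*

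**What the plan says.** Section 12.1 lists 12.1.1 to 12.1.3 under one heading of primary endpoints: sinus rhythm one minute after a single shock, after the first or second shock, and after up to two crossover shocks, the last "after crossing over from the alternative defibrillator after failing 2 consecutive full output shocks at maximum output". The Abstract, the Synopsis and section 2.1 carry three matching primary objectives. None of these places ranks them, states or splits an alpha, or says whether one or all must succeed.

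The design inputs concern the first shock:
- 5.1.1: "We hypothesize that the maximal output first shock efficacy of RBW and BTE shocks differs by more than 5" percent.
- Synopsis, Statistical and Analytical Plan: "Based on the best available literature we expect the first shock DCCV success rate to be 93% in our population".
- 12.2: "A clinically meaningful difference in first full output shock efficacy is 5" percent, followed by 544 patients (272 per group) for 80% power. The Synopsis gives 538 (269 per group).

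On crossover, 5.1.3 says "Patients who do not have success after a second full output shock will be crossed over to the other defibrillator waveform". Section 12.2 says "All analyses will be performed on an intention to treat basis". The Abstract's third aim is to "compare the DCCV efficacy of third or fourth full output shock after treatment group cross over", and the Synopsis rationale also uses the verb *compare*. The Synopsis objectives and 2.1.3 use *measure* instead. After listing all three efficacy evaluations, the Synopsis says the proportions will be compared by risk difference and risk ratio with 95% confidence intervals, and does not limit this to the first two.

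**The concern.** The plan points to the first shock as its main endpoint but never says so. A trial that is negative on the first shock and positive on first-or-second shock could be reported as positive on a primary endpoint without departing from the protocol.

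The third endpoint differs in kind. Randomisation balances the arms at the first shock. It does not balance the patients left after two failures of the assigned waveform, because who is left depends on how well that waveform worked. If one waveform is better, its failures are fewer and probably harder to convert. A contrast of crossover success between these groups mixes device effect with selection. It is nevertheless labelled primary, covered by the blanket intention-to-treat sentence, and within reach of the Synopsis comparison sentence.

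**Working it through.** **Inputs from the documents.** First-shock success 93%; difference 5 points; power 80%; 1:1 allocation; 272 per group (12.2) or 269 (Synopsis).

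**Assumptions.** Two-sided alpha 0.05 (none is stated; the 95% intervals suggest it). A null of zero difference: the Synopsis and 12.2 word the null as a difference below 5%, but step 1 shows that the planned size corresponds to a test against zero. Second-shock success among first-shock failures of 30-70% (not given).

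**1. Reproduce the plan's figure.** For 93% v 98%, pooled variance, mean rate 0.955:

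n per arm = [1.960 × √(2 × 0.955 × 0.045) + 0.842 × √(0.93 × 0.07 + 0.98 × 0.02)]² / 0.05² = [0.5746 + 0.2449]² / 0.0025 = 268.7, so 269.

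This is the Synopsis figure. Power at 272 is Φ[(0.05 × √272 − 0.5746) / 0.2910] = Φ(0.859) = 80.5%. The whole 0.05 is spent on the first shock.

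**2. Either of endpoints 1 and 2 counts.** Endpoint 2 contains endpoint 1, so the tests are correlated and were simulated (1,000,000 trials per scenario, 272 per arm, pooled z-tests), with 93% in both arms:

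| Second-shock success | Endpoint 1 or 2 falsely positive |
|---|---|
| 30% | 7.6% |
| 50% | 8.5% |
| 70% | 8.9% |

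Endpoint 1 alone gives 5.1%.

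**3. Both must succeed.** With equal second-shock success s, the true difference on endpoint 2 is 0.05 × (1 − s): 3.5, 2.5 and 1.5 points for s = 30, 50 and 70%. At 93% v 98%:

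| Second-shock success (93% arm v 98% arm) | Power for both |
|---|---|
| 30 v 30% | 66% |
| 50 v 50% | 50% |
| 70 v 70% | 30% |
| 30 v 50% | 75% |
| 40 v 60% | 71% |
| 50 v 70% | 65% |
| 50 v 80% | 72% |
| 70 v 90% | 54% |
| 30 v 70% | 80% |

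The like-for-like comparator is the simulated first-shock power, 83%, not the 80.5% from the formula.

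**4. Size of the crossover groups.** Expected number = 272 × first-shock failure × (1 − s):
- at 93%: 272 × 0.07 = 19.0 failures, leaving 13.3, 9.5 or 5.7 crossovers for s = 30, 50 or 70%;
- at 98%: 272 × 0.02 = 5.4 failures, leaving 3.8, 2.7 or 1.6.

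Exact (Clopper-Pearson) 95% intervals for crossover success are wide: 12-88% for 3 of 6, and 19-75% for 6 of 13.

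**The case against.** *The first shock is plainly the main endpoint.* That is the natural reading of 5.1.1 and 12.2, and the first-shock sample size and power are unaffected by this point. But the label primary is given to three endpoints, so the intention needs stating.

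*Inflation needs a success rule that the plan does not contain.* This stands. The documents never say that a win on any one endpoint makes the trial positive. The 7.6-8.9% is what follows under that reading. A reader might infer an established error rate of 14.3%, from 1 − 0.95³. The documents do not support that: it assumes three independent tests and an any-win rule, whereas endpoints 1 and 2 overlap.

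*The third endpoint is only descriptive.* The *measure* wording in the Synopsis objectives and 2.1.3 allows this, and the most realistic harm is a descriptive result mislabelled as a primary comparison. A reader might go further and say that no between-arm comparison is planned for it. The Synopsis does not support that, because its comparison sentence follows all three evaluations without exception.

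*The schedule shows that only the first shock counts.* A reader might infer this from the row "ECG or Monitor 1 minute after 1 st shock". It is weak evidence: 12.1 requires the rhythm to be recorded after each shock, and 5.1.3 requires each outcome to be known before the next shock. The row is better read as incomplete, and nothing here rests on it.

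**Conclusion.** The point holds. Three endpoints are primary without an order or decision rule, and the design supports only the first. If either of the first two can carry the trial, the false-positive chance is 7.6-8.9% instead of about 5%. If both must, error is controlled but 80% power is not assured: 30-66% with equal second-shock success, and 54-80% in the examples where the better waveform is also better on the second shock. These figures rest on two-sided 0.05, a null of zero difference and assumed second-shock rates.

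The objection to the third endpoint needs no such assumptions: its groups are formed by outcome after randomisation, so it is not an intention-to-treat comparison. It would rest on about 6-13 patients per arm at 93%, and 2-4 in an arm at 98%.

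This should be changed, but it does not make the trial underpowered for its first-shock question.

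**What to change.** 1. In 12.1, name sinus rhythm one minute after the first shock as the single primary endpoint, tested at two-sided 0.05.
2. Test sinus rhythm after the first or second shock, at two-sided 0.05, only if the first test is significant.
3. Report crossover success by direction as a proportion with an exact 95% interval and no between-arm test. Use *measure* for it in the Abstract, Synopsis and objectives. Exempt it from the intention-to-treat sentence in 12.2 and from the comparison sentence in the Synopsis.
4. The Synopsis plans one interval analysis at 50% enrollment with no alpha stated. State that it does not test efficacy, or account for its alpha; otherwise the 0.05 in item 1 does not hold.

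The cost is wording only. The sample size is unchanged, and first-shock power stays at 80.5% by formula, subject to item 4. The downside is that the first-or-second-shock endpoint can be claimed only after the first, so its chance of a claim is the power for both given above, and crossover success supports no formal claim. A Bonferroni split over endpoints 1 and 2 would also be valid, but at 0.025 first-shock power by the same formula falls to Φ[(0.8246 − 2.241 × 0.2932) / 0.2910] = 71.8%.

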Study Objective(s):	
Primary:
 
 1. To compare the efficacy of a single 200J RBW shock and a single 360J BTE shock 2. To compare the efficacy of one or two consecutive 200J RBW or 360J BTE shocks 3. To measure the efficacy of cross over from RBW to BTE or BTE to RBW after failing 2 consecutive full output shocks with the first waveform 
Secondary:
 
 1. To compare the frequency of adverse events after one or two 200J RBW or 360J BTE shocks
Test Product(s)/Agent(s):	
 1. Zoll Series R Defibrillator (RBW shock waveform, maximum output 200J) 2. Physiocontrol Lifepak 15 or 20 Defibrillator (BTE shock waveform, maximum output 360J)
Study Design:	Single center, investigator-initiated, open label prospective randomized controlled trial
Participant Population Key Criteria for Inclusion and Exclusion:	
Inclusion Criteria:
 
 ▪ Adults aged ≥ 18 years of age in AF scheduled to undergo DCCV or catheter ablation with expected DCCV 
Exclusion Criteria:
 
 ▪ Patients with arrhythmias other than AF, hemodynamically unstable AF, untreated hyperthyroidism, known or suspected pregnancy, those in another trial. Patients will be required to have received sufficient anticoagulation or computed tomography angiography scan or transesophageal echocardiogram documenting the absence of intracardiac thrombi.
Number of Participants:	A total of 560 unique study subjects will be enrolled.

A Pragmatic Randomized Clinical Trial Comparing Rectilinear Biphasic Waveform and Biphasic Truncated Exponential Waveform Shocks for Cardioversion of Atrial Fibrillation (Zoll vs Lifepak-RCT) |

PI: [name]

Study Duration:	Each subject's participation will last from screening until 1 minute after the final DCCV shock is delivered.
Study Phases:	
 1. Screening: Patients arriving in AF scheduled to undergo DCCV or AF ablation with possible DCCV at an Inova site of care will be screened in the peri-procedure holding area. 2. Intervention: Patients will be randomized to a Zoll or Lifepak defibrillator to perform the DCCV. All shocks will be full output (200J for Zoll shocks and 360J for Lifepak shocks). Follow up will be assessment and documentation of rhythm 1 minute after the last shock is delivered.

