2.2 Secondary Objectives

- 2.2.1 To compare the frequency of adverse events after one or two 200J RBW or 360J BTE shocks. Patients undergoing cross-over will be excluded from this analysis.

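### The only planned safety comparison leaves out patients who failed two shocks on the assigned device, and the synopsis states that exclusion for the skin item only

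*Combined protocol and SAP*

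**What the plan says.** Two sections in the body of the protocol agree. Section 2.2.1 gives the secondary objective, the frequency of adverse events after one or two assigned-device shocks, and adds "Patients undergoing cross-over will be excluded from this analysis". Section 12.1.4 lists three components (skin, arrhythmic events, pacemaker/ICD dysfunction) and closes with "The secondary safety endpoint will be assessed only among patients who do not cross-over from one defibrillator to the other".

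The synopsis differs. Its secondary objective, "To compare the frequency of adverse events after one or two 200J RBW or 360J BTE shocks", limits the shocks but excludes no patients. Under Safety Evaluations, item 1 carries the exclusion: "Number of patients with skin redness, pain or discomfort under the shock electrodes (excluding those with cross-over". Items 2 and 3 do not: "Number of patients with arrhythmic events (asystole, atrioventricular block, transient bradycardia or ventricular arrhythmia) within 10 minutes of the last DCCV shock" and "Frequency of pacemaker or ICD dysfunction after shock among patients with prior pacemaker or defibrillator implant".

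On the analysis population, the synopsis statistical section says "The analysis will be performed on the intention-to-treat population", and section 12.2 extends the intention-to-treat basis to all analyses. Neither mentions an exception for safety.

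Sections 5.1.3 and 10.1.2 define crossover as the step taken after a second unsuccessful shock on the assigned device. Safety is observed late. The schedule has "Adverse Event Assessment 10 minutes after shock or at conclusion of procedure", and section 9.2.1 places the skin check at least 10 minutes after the final shock.

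**The concern.** Whether a patient enters the safety set is decided after randomisation, by the result of primary endpoint 12.1.2. The trial's hypothesis (5.1.1) is that the devices differ in efficacy. If they do, the two arms lose different numbers of patients, and those lost have each received the maximum of two assigned-device shocks. What remains is no longer a comparison of the randomised groups, and nothing else in the plan compares the devices on safety.

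The second problem is the inconsistency. For the arrhythmia and pacemaker/ICD items the body excludes crossover patients and the synopsis does not. Treatment is unblinded, so an analyst could defend either denominator after seeing the data. Safety is half of the trial's stated rationale (1 and 1.3), so its analysis set should be fixed in advance.

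**Working it through.** **Sets by component, as written**

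| Component | Synopsis | 2.2.1 and 12.1.4 | 12.2 |
|---|---|---|---|
| Skin | crossovers excluded | crossovers excluded | intention to treat |
| Arrhythmic events | no exclusion | crossovers excluded | intention to treat |
| Pacemaker/ICD | no exclusion | crossovers excluded | intention to treat |

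For arrhythmia, the synopsis reading adds the events that follow a crossover patient's last shock. That is shock 3 or 4, given by the other device.

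**Inputs.** From 12.2: first-shock success 93%, a 5-point difference of interest, 272 per arm. The second arm's 98% is 93% plus 5 points. As a check, 93% vs 98% at two-sided 5% (assumed) and 80% power gives 268.7, so 269 per arm and 538 in total. That is the synopsis figure, and it is close to the 544 in 12.2. The documents give no second-shock success rate and no adverse event rates, so everything below on those is assumed.

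**Patients excluded.** With p the first-shock success and s the second-shock success, the number excluded per arm is 272 × (1 − p) × (1 − s).

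- s = 30%: 272 × 0.07 × 0.7 = 13.3 vs 272 × 0.02 × 0.7 = 3.8
- s = 50%: 9.5 vs 2.7
- s = 70%: 5.7 vs 1.6
- p = 93% in both arms, s = 50%: 9.5 vs 9.5

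**Effect on the comparison.** Let a1, a2 and a3 be the event risks in patients who need one shock, who need two, and who cross over.

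- All treated, by assigned device: p·a1 + (1 − p)·s·a2 + (1 − p)(1 − s)·a3
- Non-crossover: [p·a1 + (1 − p)·s·a2] / [1 − (1 − p)(1 − s)]
- One-or-two-shock value: the all-treated formula with a3 = a2, so that only assigned-device shocks count. It cannot be observed in crossover patients, because the assessments follow the last shock.

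*Skin, equal devices, a1 = 20%, a2 = 40%, s = 50%.*

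- One-or-two-shock: 0.93 × 20 + 0.07 × 40 = 21.4% vs 0.98 × 20 + 0.02 × 40 = 20.4%, a difference of 1.0 point.
- Non-crossover: (18.6 + 1.4)/0.965 = 20.73% vs (19.6 + 0.4)/0.99 = 20.20%, a difference of 0.5 point (0.3 to 0.7 for s from 30% to 70%).
- All treated, with crossover shocks adding independent risk: a3 = 1 − 0.6 × 0.8 = 52% after one and 1 − 0.6 × 0.6 = 64% after two. The difference is 1.3 to 1.6 points (1.2 to 1.8 over the same range of s).
- Standard error: √(0.214 × 0.786/272 + 0.204 × 0.796/272) = 3.5 points.

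*Arrhythmia, a1 = 2%, a2 = 4%, a3 = 6–8%, s = 50%.* The non-crossover difference is 0.05 point and the all-treated difference 0.15 to 0.20, with a standard error of about 1.2. Excluded events number 9.52 × 0.06 to 9.52 × 0.08 = 0.6 to 0.8 in one arm and about 0.2 in the other.

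*Direction.* If the less effective device is also 1.5 times as harmful to skin, the one-or-two-shock difference is 11.7 points and the non-crossover set shows 10.9. If the more effective device is the more harmful, −9.2 becomes −9.6. The exclusion can shrink or enlarge a real difference.

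*Bracketing.* In the examples where the switch adds risk and the devices are equal, the two sets err on opposite sides of the one-or-two-shock value. This is not guaranteed. If crossover patients' skin risk is only 10–20%, the all-treated difference is 0.25 to 0.5 point, and both sets fall below 1.0.

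**The case against.** The exclusion is deliberate, and it is stated beside both the objective and the endpoint. The objective concerns events after one or two shocks. A crossover patient goes on to a third and perhaps a fourth shock from the other device, and the planned assessments come after the last one, so they cannot isolate the assigned device's effect. This stands, and it is the reason to keep the non-crossover analysis.

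The synopsis sentence on intention to treat follows the first-shock sample size and may refer to efficacy alone. That is a fair reading. Section 12.2 has no such limit, although a reader could take 12.1.4 as a specific rule overriding a general one.

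The all-treated set is not clearly more accurate. In the skin example it misses the one-or-two-shock value by +0.3 to +0.6 point, against about −0.5 for the planned set. If the target were harm per shock, the true difference in that example would be zero and the planned set would be nearer. The first part stands and argues for showing both analyses. On the second, the stated objective is events after one or two shocks, not risk per shock.

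Adverse events in crossover patients are still monitored and summarised (13.2, 13.2.1). That is true, but it is not a comparison between arms.

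**Conclusion.** The concern holds. The textual part is certain: the synopsis and the body give different sets for two of the three safety components, and 12.2 carries no exception for the exclusion in 2.2.1 and 12.1.4. The analytical part also holds, but its size is modest. The sole safety comparison is conditioned on failing a primary endpoint. Under the assumed rates the resulting distortion is about half a point for skin (standard error about 3.5 points) and about 0.05 point for arrhythmia (standard error about 1.2). The direction depends on the unknown risk in the excluded patients. These sizes rest on a 5-point first-shock difference, second-shock success of 30–70% and invented event rates. The change is worth making because the analysis set is ambiguous and the remedy is cheap, not because a large bias is expected.

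**What to change.** Align the synopsis (secondary objective, Safety Evaluations, statistical section) with 2.2.1, 12.1.4 and 12.2, so that all three safety components use the same stated sets. Suggested wording:

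*Each safety component will be compared (a) in patients who do not cross over and (b) by assigned device in all randomised patients who receive at least one shock, using the assessments already planned. Both results will be reported side by side, and events in crossover patients will be listed by assigned arm.*

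The sponsor should state in advance which of the two leads. Section 12.2 and the synopsis statistical section should say that both sets are exceptions to strict intention to treat, since (b) also omits randomised patients who receive no shock.

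The cost is wording in these sections and one additional table. The assessments in the schedule and in 9.2.1 suffice, and no check between shocks is added. The drawback is that (b) charges some of the other device's harm to the assigned arm. Keeping (a) beside it serves the device-attribution question.
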